In the prior cycle of this Program Project, a number of findings from diffusion tensor imaging and fluid biomarkers associated with inflammation were identified as predisposing to delirium. However, it is not clear whether those biomarkers might have been associated with preclinical AD pathology, vulnerable aging, or other known pathologies. Using modern magnetic resonance imaging (MRI) techniques, we have identified an "AD-Signature" of cortical atrophy and hippocampal hyperactivation as biomarkers of prodromal or preclinical AD. In addition, measures of changes in the brain that are associated with age-related cognitive decline in the absence of neurodegenerative or cerebrovascular disease can be detected as a "Vulnerable Aging-Signature" of cortical atrophy and reduced frontoparietal functional connectivity. Therefore, the overarching goal of Project 3 is to examine whether neuroimaging biomarkers of preclinical AD or vulnerable aging are predictive of delirium, delirium severity, and complicated delirium (i.e., delirium with LTCD), and to link these neuroimaging biomarkers to molecular biomarkers of pathology measured in the cerebrospinal fluid (CSF) and plasma. The Specific Aims are: 1) to determine in people with evidence of preclinical AD (i.e. patients with abnormal CSF AD biomarker levels of tau and beta-amyloid or classified as amyloid-positive in PET imaging) whether ADrelated brain atrophy or network dysfunction are associated with delirium, delirium severity, or LTCD; 2) to determine in people without evidence of preclinical AD (i.e. patients with normal AD biomarkers) whether vulnerable aging-related brain atrophy or network dysfunction are associated with delirium. delirium severity, or LTCD; and 3) to investigate whether longitudinal cortical atrophy (measured preoperatively and one year after surgery) due to preclinical AD or vulnerable aging is associated with postoperative LTCD or complicated delirium. To test these hypotheses, we will leverage the existing SAGES I cohort (N=560 total, n=126 with longitudinal MRI), augmented by new CSF (or PET) and MRI data collected in 148 SAGES I probability sampled patients (SAGES I SELECT) (74 with delirium, 74 without) about four years after their surgery, and a new SAGES II cohort (N=460), of which 180 patients will have both CSF (or PET) and MRI collected pre-operatively. The long-term objective of this Project is to improve the pathophysiological understanding of brain vulnerability to delirium in order to inform prevention strategies and, ultimately, pathophysiological-based treatments.

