
A.2.4 Project 4

In the previous Program Project, we have demonstrated that about half of people who develop postoperative delirium return to preoperative baseline cognitive performance levels within about 8 weeks of surgery, but about a third of those who develop postoperative delirium show accelerated cognitive decline out to 36 months following surgery. Our working definition of complicated delirium is delirium associated with a higher degree (or pace) of cognitive decline in long-term follow-up (i.e., $\geq 2-3$ years). In this sub-group, the pace is similar to that observed among persons with mild cognitive impairment. Defining complicated delirium in terms of long-term cognitive decline is problematic since the outcome cannot be detected for years. Therefore, this Project will help identify predictors of complicated delirium to assist with early identification. Our aims are: (1) to identify predictors for early identification of complicated delirium using an expert panel, (2) identify predictors for early identification

of complicated delirium using empiric data, and (3) to validate the predictive models in an independent sample (external validity) and against clinical outcomes (predictive validity). We will use information that is potentially available before, during and immediately following surgery. We will also evaluate models using biomarkers derived from cerebrospinal fluid, serum, neurophysiologic measures, and neuroimaging obtained before surgery. We will accomplish our aims with (a) the insights of experts in delirium in a modified Delphi process; (b) secondary data analysis of the rich data already collected in the SAGES I cohort, and (c) validation with new observational and clinical data collected within the context of the new SAGES II cohort study. We will develop multiple models including preoperative, perioperative, and postoperative predictor variable sets, and their combination. The ultimate goal of this work is to improve delirium recognition and treatment by clinicians, and heighten the prognostic importance of delirium among clinicians, their patients, and policy makers.

A.2.5 Project 5

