B. Statistical Considerations

B.1. Sample Size Justification:

Our sample sizes were chosen based on an iterative process involving determining the size of the target population eligible, feasibility constraints, and then verifying adequate power to test the hypotheses across all of our proposed studies for Projects 1-5. Through these detailed considerations, and input from our expert statisticians, we have been able to verify adequate power to address all of our study aims with the proposed sample sizes for the SAGES I SELECT subsample (N=148), the SAGES II cohort (N=460) and the SAGES II subsample (N=180). Power has similarly been verified for all aims of each project. For SAGES II, approximately 50% of the cohort will be enrolled at BIDMC and 50% at BWH. The data, however, will be analyzed together. Computations allow for two-sided type-I error probability 0.05 and to take into account cumulative attrition consistent with our experience in this population. We use multiple imputation to account for missing data where appropriate.

B.1.2. Experimental design and sampling: general considerations

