Aim 1: Determine in people with evidence of preclinical AD whether AD-related brain atrophy or network dysfunction are associated with delirium, delirium severity, or LTCD. Power Analysis: For H1a, the SAGES II MRI sample has 180 subjects. We expect 32% to have abnormal CSF AD biomarkers⁶⁵ (n=57). Based on published rates⁶⁶, we expect 36% of the AD biomarker positive sample to develop delirium. From our previous studies, the mean of AD-signature cortical thickness is 2.49mm (SD 0.14). We assume this distribution for the non-delirium patients. A conservative effect size of 5%

decrease in cortical thickness for the delirium patients yields a mean of 2.37mm. With type-I error of 0.05, we obtained a power estimate of 0.87. For H1b, the SAGES I SELECT cohort has 148 patients. With 34% assumed to have abnormal CSF AD biomarkers, this yields 44 subjects. We assume that for those without delirium and no LTCD, cortical thickness has the same distribution as stated above and that those with both delirium and LTCD would have even greater atrophy than delirium alone; thus a slightly increased but still conservative threshold of 7% decrease yields 2.37mm. The power estimate is 0.97 given this sample and relative difference of the two cortical thickness means. For H1c, the combined sample size would be 48+44=92. The estimated pairwise Spearman correlation coefficient among the MRI and CSF biomarker variables would be statistically significantly detected at the level of correlation equal to at least 0.4 from the null estimate of 0.1, and power of 0.87.

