Aim 2. Determine in people without evidence of preclinical AD whether vulnerable aging-related brain atrophy or network dysfunction are associated with delirium, delirium severity, or LTCD. Power Analysis: We expect 68% of the 180 SAGES II subjects for H2a will have normal CSF AD biomarkers, yielding a sample size of 123. Among these, we expect 24% with delirium (30 with delirium, 93 without). From prior work,⁶⁷ we assume that the Aging-signature cortical thickness for the power analysis is 1.94mm (SD 0.18) for the non-delirium patients. A conservative effect size of 6% decrease in cortical thickness for the delirium patients yields a mean of 1.82 mm. With type-I error of 0.05, we obtained a power estimate of 0.88. For H2b, the SAGES I SELECT cohort has 148 patients. With 66% assumed to have normal CSF AD biomarkers, this yields 88 subjects. We assume that for those without delirium and no LTCD, vulnerable aging cortical thickness has the same distribution as stated above and that those with both delirium and LTCD would have even greater atrophy than delirium alone; thus a slightly increased but still conservative threshold of 7% decrease yields 1.80mm. The power estimate is 0.94 given this sample and the effect size of 7% in relative difference of the two cortical thickness means. For H2c, the combined sample size would be 123+84=207. The estimated pairwise Spearman correlation coefficient among the inflammatory biomarkers from Project 2 and the vulnerable aging MRI variables would be statistically significantly detected at the level of correlation equal to at least 0.3 from the null estimate of 0.1, and the power of 0.85. At the correlation level of 0.3, power is 0.85.

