Aim 3. Investigate whether cortical atrophy due to preclinical AD or vulnerable aging is associated with postoperative LTCD or delirium with LTCD. Power Analysis: For H3a, using estimates from prior work,⁶⁷ the estimated mean prevalence of cortical atrophy of either preclinical AD or aging is 19.3%. We assume this estimate for the no delirium group, and a relative risk of 2.5 of having cortical atrophy for the delirium group. Of the 126 subjects, 22% (n=28) subjects had delirium, and 98 did not. Given these estimates, the power is 0.82. For H3b, among those with delirium and LTCD relative to those with no delirium, and no LTCD, we assume that the conditional probability of having LTCD given that one has delirium is 70%, and the conditional probability of having LTCD given that one does not have delirium is 20%. Given these estimates, the joint frequency distribution is N=20 for those with both conditions of delirium and LTCD, and N=78 for those with neither condition. The expected relative risk would be higher in this comparison than 2.5 in H3a. With a power of 0.81, and the given sample size of 126, we could detect a statistically significant relative risk of at least 2.75 at type-I error of 0.05.

Project 4

Aim 1a: Mount a Modified Delphi Process Involving Delirium Experts to Identify Predictors of Delirium and Cognitive Decline Following Delirium (Complicated Delirium) for Early Identification. Statistical Power Considerations: N/A

Aim 1b. Operationalize and Evaluate the Accuracy of the Predictors for Complicated Delirium. Statistical Power Considerations. Our pilot data suggest we might expect a correlation between model-implied cognitive slope and observed cognitive slope of about r = .54. With 375 patients in the model development sample and 185 in the model testing sample, we used Monte Carlo procedures to determine that we will have an 80% probability of obtaining a correlation between .48 and .60 in both the model development and model testing samples. Therefore, we believe this aim is adequately powered to generate a reasonable probability of identifying a replicable model.

Aim 2a: Identify and Cross-Validate Predictors of Complicated Delirium. Statistical Power

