Considerations. Similar to Aim 1b, with 375 patients in the model development sample and 185 in the model testing sample, we will have an 80% probability of obtaining a correlation between 0.48 and 0.60 in both the model development and model testing samples. Therefore, we believe this aim is adequately powered to generate a reasonable probability of identifying a replicable model. Aim 2b. Harmonize the Expert Panel-Derived Predictive Models from Aim 1 with Empirically Derived Predictors Models from Aim 2a. Statistical Power Considerations: N/A

Aim 2c. Evaluate the Correlation of the Harmonized Models with Observed Long-Term Cognitive Decline Following Delirium. Statistical Power and Sample Size Considerations. If we assume that any of the complicated delirium definitions identifies 33% of the SAGES I delirious sample (N=134) as probable members of complicated delirium group, we have an estimated prevalence of complicated delirium of $(0.33 \times 134/560 = 44/560 = 8\%)$. We will be able to detect predictors where the underlying correlation (tetrachoric correlation, *r*_{tet}) between the predictor and complicated delirium assignment is between a small and moderate effect (minimal detectable correlation, *r*_{tet} = .28), a medium effect size in Cohen's effect size taxonomy. Thus, this aim is adequately powered to replicate predictors that have at least medium effect size, which should be clinically relevant and achievable.

Aim 3a. Replicate SAGES I Findings with Predictive Model in Newly Acquired SAGES II Sample (External Validation). Statistical Power and Sample Size Considerations. With 400 participants, it might be expected that power will be lower than when the sample size is 560 (Aim 2c). However, the SAGES II sample will be enriched for baseline cognitive impairment and as a consequence we can expect a higher prevalence of delirium in this subgroup (because, as described in our preliminary studies, baseline cognitive level is the most powerful and dominant risk factor for delirium). Assuming a prevalence of delirium of 24% and a prevalence of complicated delirium among the delirious of 33%, the minimum detectable association for prognostic factors is $r_{tet} = .28$. Thus, this aim is adequately powered to replicate predictors that have a medium to large effect size.

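### Project 3's power for H3b assumes 70% LTCD among delirious patients while Project 4 uses one third for the same construct; H1b and H2b give no cell sizes for the same contrast

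*Protocol*

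**What the plan says.** **H3b (Protocol B.1.3, Project 3, Aim 3).** The sample is 126 SAGES I patients with longitudinal MRI, 28 with delirium and 98 without. The protocol states that "we assume that the conditional probability of having LTCD given that one has delirium is 70" per cent and that "the conditional probability of having LTCD given that one does not have delirium is 20" per cent. It derives 20 patients with both conditions and 78 with neither, and states power 0.81 for a relative risk of at least 2.75. Atrophy prevalence in the reference group is 19.3%.

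**The same construct elsewhere.** Section A.2.3 speaks of "complicated delirium (i.e., delirium with LTCD". Section A.2.4 reports from the previous Program Project that "about a third of those who develop postoperative delirium show accelerated cognitive decline out to 36 months following surgery". In B.1.3, Project 4, Aim 2c assumes 33% of the 134 delirious SAGES I patients, giving a prevalence of 44/560 = 8%. Aim 3a uses "a prevalence of complicated delirium among the delirious of 33" per cent for SAGES II.

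**H1b and H2b (B.1.3, Project 3, Aims 1 and 2).** Both compare patients who have delirium and LTCD with patients who have neither, within a biomarker stratum of SAGES I SELECT. Neither gives an LTCD share or the size of the two groups. H1b has 44 patients and power 0.97, and says "thus a slightly increased but still conservative threshold of 7% decrease yields 2.37mm". For H2b: "With 66% assumed to have normal CSF AD biomarkers, this yields 88 subjects", with power 0.94.

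**Error rate (B.1).** "Computations allow for two-sided type-I error probability 0.05".

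**The concern.** H3b's power depends on how many delirious patients fall in the delirium-plus-LTCD cell, which is the smaller of the two. Moving from 70% to one third more than halves that cell, from 20 to 9. Project 3 and Project 4 use the two rates for what A.2.3 treats as one construct, in the same parent cohort, without comment.

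H1b and H2b raise a related problem. A contrast between two of the four delirium-by-LTCD cells leaves out the patients in the other two, yet the stated powers look as though almost nobody was left out.

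Section B.1 says adequate power was verified for all aims, and these three figures support that claim for Project 3's delirium-with-LTCD questions. If they are too high, a null result would be read as more informative than it is.

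**Working it through.** All tests are two-sided at 0.05.

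**1. Reproduce H3b.** Proportions are 0.193 and 0.193 × 2.75 = 0.531. Cells are 0.70 × 28 = 19.6, so 20, and 0.80 × 98 = 78.4, so 78. Fisher's exact test by full enumeration gives 0.815 (stated 0.81). The same method for H3a (28 v 98, relative risk 2.5) gives 0.822 (stated 0.82). Fisher is therefore a good match for the method used.

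**2. H3b at one third.** 0.33 × 28 = 9.24, so 9 v 78.

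| Cells | Fisher | Chi-square (enumerated) |
|---|---|---|
| 20 v 78, RR 2.75 | 0.815 | 0.842 |
| 9 v 78, RR 2.75 | 0.546 | 0.628 |
| 9 v 78, RR giving 80% power | about 3.4 | about 3.2 |

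**3. Reproduce H1b and H2b.** Two-sample t-test, noncentral t. Each range covers the exact 7% fall and the rounded mean.

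- H1b: 7% of 2.49 mm is 0.174 mm, so the mean is 2.32 mm and d = 0.174/0.14 = 1.245 (1.214 from the rounded mean). All 44 as 22 v 22 gives 0.976-0.981; 15 v 29 at the exact 7% gives 0.969. Stated: 0.97.
- H2b: 7% of 1.94 mm is 0.136 mm, so d = 0.136/0.18 = 0.754 (0.778 at the printed 1.80 mm). All 88 as 44 v 44 gives 0.938 at the exact 7%; 42 v 42 at 1.80 mm gives 0.941. Stated: 0.94.

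Several splits land on the stated figures, but all use the whole stratum or nearly all of it.

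**4. H1b and H2b with only the compared cells.** SAGES I SELECT is 74 with and 74 without delirium. The protocol gives no split within a biomarker stratum, so 1:1 is my assumption. The 20% LTCD rate without delirium is taken from H3b.

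| Case | H1b cells | H1b power | H2b cells | H2b power |
|---|---|---|---|---|
| Stated | not given | 0.97 | not given | 0.94 |
| 70%/20%, printed N (44, 88) | 15 v 18 | 0.92-0.93 | 31 v 35 | 0.85-0.87 |
| 33%/20%, printed N (44, 88) | 7 v 18 | 0.74-0.76 | 15 v 35 | 0.67-0.70 |
| 33%/20%, from 148 (50, 98) | 8 v 20 | 0.80-0.82 | 16 v 39 | 0.70-0.73 |

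If H2b used 84 rather than 88, one third would give 14 v 34 and 0.64-0.67.

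**5. Input arithmetic.**

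- 2.49 × 0.93 = 2.32 mm. The printed 2.37 mm is the 5% figure used for H1a. At 2.37 mm, 22 v 22 gives only 0.79, so the stated 0.97 must have used a true 7% fall.
- 0.34 × 148 = 50 and 0.66 × 148 = 98, not 44 and 88. 0.34 × 128 = 44 and 0.66 × 128 = 84. The 88 fits neither N, and H2c uses 84.
- H1c adds 48 for the SAGES II stratum, where H1a states 57.

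**6. If 70% were kept in Project 4.** 0.70 × 134/560 = 94/560, about 17% in place of 8%.

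**The case against.** Four points on the other side carry weight.

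*Different horizons.* The one third in A.2.4 is decline out to 36 months, while LTCD in SAGES I SELECT runs over at least 8 years. Project 4's 33% is itself conditional, and B.2.3 (Project 4, Aim 2c) leaves the accelerated-decline threshold to be defined. A higher share is conceivable with longer follow-up, or among biomarker-positive patients. This stands as a possible reason for two rates, but the protocol does not offer it. It means one third cannot be declared the right value for Project 3.

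*Planned models.* B.2.3 analyses GCP as a continuous repeated measure with delirium status and an interaction, and drops nobody into two cells. A reader might infer that the true power of the Project 3 analyses is 0.55 to 0.8. The documents do not support that: the recalculation speaks only to the simplified comparison the protocol chose for its power statements.

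*H1b and H2b.* A reader might also infer that these assume every delirious patient has LTCD. No rate is stated there, and other splits also come close to 0.97 and 0.94, so this remains a back-calculation. The 1:1 split is also doubtful: Project 1, Aim 3 cites higher biomarker positivity in delirium (70-80% against 40-50%).

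*Legacy sample size.* B.1.2 discloses that analyses were originally powered on 128 in SAGES I SELECT and expects the larger sample to do better. That explains 44 and 84. It does not explain 88, or why 44 and 88 are printed as following from 148. It also gives no help to H3b, whose 126 patients are an existing sample.

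**Conclusion.** The point holds for H3b as an unreconciled contradiction. At the protocol's own one-third rate, its two-group calculation gives about 0.55-0.63 rather than 0.81, and the relative risk detectable with 80% power rises from about 2.75 to about 3.2-3.4. This rests on the 20% LTCD rate without delirium and the 19.3% atrophy prevalence, both kept as stated.

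For H1b and H2b the finding is that the cells are unstated and the powers do not follow from the contrast described. Even at the plan's own 70%/20% they are about 0.92-0.93 and 0.85-0.87; at one third they are about 0.74-0.82 and 0.67-0.73. Both results depend on the assumed 1:1 delirium split, and the one-third ranges cover the printed and the 148-based counts.

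The slips in thickness and sample counts need no assumption. No enrolment number, endpoint or procedure is affected.

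**What to change.** 1. Use one rate of LTCD given delirium in Projects 3 and 4, or justify different rates by follow-up horizon or definition. If 70% is kept for the same construct, Project 4's 8% prevalence becomes about 17%.
2. State the cell sizes for H1b, H2b and H3b, counting only patients in the two compared cells, and state the assumed delirium split within each biomarker stratum.
3. Correct 2.37 mm to 2.32 mm for the 7% fall in H1b.
4. Use one N throughout: 148 gives 50 and 98; 128 gives 44 and 84. Reconcile H1c's 48 with H1a's 57.
5. Restate the three powers over the range from one third to 70%, with H3b at one third given as about 0.55-0.63, and say that they refer to the simplified two-group comparison.

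The cost is revised wording and one re-run of the power calculations. Data collection does not change, but the stated powers will be less favourable.

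### Protocol B.1.3, Project 4, Aim 3a: the minimum detectable tetrachoric correlation of .28 is carried over from N=560 to N=400 at an unchanged outcome prevalence, so it is too small

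*Protocol*

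**What the plan says.** Protocol B.1 sets the general level: "Computations allow for two-sided type-I error probability 0.05". In B.1.3, Project 4, Aim 2c takes one third of the 134 delirious SAGES I patients as complicated cases. That is 44 of 560, or 8%, and the aim reports a minimum detectable tetrachoric correlation of .28.

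Aim 3a moves to SAGES II and raises the obvious worry itself: "With 400 participants, it might be expected that power will be lower than when the sample size is 560". It answers that SAGES II is enriched for baseline cognitive impairment, so delirium should be more frequent. The calculation then starts "Assuming a prevalence of delirium of 24% and a prevalence of complicated delirium among the delirious of 33%, the minimum detectable association" and again reports .28. Neither aim states the power or how common the predictor is.

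B.1.2 explains that the power figures were first worked out for 400 SAGES II patients, that the cohort is now 460, and that the stated power should therefore be exceeded.

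Aims 1b and 2a of the same project give a different kind of figure. The pilot suggests a "correlation between model-implied cognitive slope and observed cognitive slope of about r = .54". The text continues "With 375 patients in the model development sample and 185 in the model testing sample, we used Monte Carlo procedures" and claims an "80% probability of obtaining a correlation between .48 and .60 in both the model development and model testing samples".

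**The concern.** For a given test, outcome prevalence and predictor prevalence, the smallest detectable association grows as the sample shrinks. Aim 3a has 160 fewer patients than Aim 2c (560 - 400), which is 29% fewer. Its outcome prevalence is the same, yet so is its answer. The enrichment argument could in principle close the gap, but only through a higher delirium rate. The 24% entered is the SAGES I rate (134/560 = 23.9%), so the argument never reaches the calculation.

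At stake is how a failed replication is read. Aim 3a is the external validation of the predictors found in SAGES I. A reader who takes .28 at face value will think a predictor of that strength is more likely to replicate than it is.

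**Working it through.** **Inputs from the Protocol.** Two-sided 5% (B.1). Outcome prevalence 44/560 = 0.0786 (Aim 2c) and 0.24 x 0.33 = 0.0792 (Aim 3a). N = 560 (Aim 2c), 400 (Aim 3a) and 460 (current SAGES II size, B.1.2).

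**Inputs assumed.** Power 80%. Predictor prevalence q varied from 20% to 50%.

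**Method.** Let d be the outcome prevalence and r the tetrachoric correlation. The probability of having both predictor and outcome is the bivariate normal probability p11 = Φ2(z_q, z_d; r). The outcome risk is a = p11/q with the predictor and b = (d - p11)/(1 - q) without it. With n1 = Nq and n2 = N - n1,

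power = Φ{ (a - b - 1.96 s0) / s1 },

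where s0² = d(1 - d)(1/n1 + 1/n2) and s1² = a(1 - a)/n1 + b(1 - b)/n2.

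**Step 1: worked example at r = .28, q = 25%.**

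- N=560: a = 0.1375, b = 0.0589, s0 = 0.0263, s1 = 0.0313. Power = Φ{(0.0786 - 0.0515)/0.0313} = 0.81. This supports Aim 2c.
- N=400: a = 0.1384, b = 0.0595, s0 = 0.0312, s1 = 0.0371. Power = Φ{(0.0789 - 0.0612)/0.0371} = 0.68.
- N=460: the same a and b, s0 = 0.0291, s1 = 0.0346. Power = Φ{(0.0789 - 0.0570)/0.0346} = 0.74.

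**Step 2: solve for r at 80% power.**

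| Predictor prevalence | N=560 | N=400 | N=460 |
|---|---|---|---|
| 20% | 0.285 | 0.332 | 0.311 |
| 25% | 0.278 | 0.324 | 0.304 |
| 33% | 0.272 | 0.319 | 0.298 |
| 50% | 0.275 | 0.327 | 0.304 |

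Aim 2c's .28 reproduces and Aim 3a's does not. Power at r = .28 over the same predictor prevalences is 0.67 to 0.70 at N=400 and 0.72 to 0.75 at N=460. A rough check by square-root scaling agrees: .28 x √(560/400) = 0.33 and .28 x √(560/460) = 0.31.

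**Step 3: sensitivity to the assumptions.** Predictor prevalence was varied from 5% to 80%, and unpooled, arcsine and log-odds-ratio tests were also tried. The smallest two-sided value at N=400 was about 0.316. A one-sided test comes near .28 at N=400 (about 0.285 at q = 40%), but the same setting gives 0.24 at N=560, so it cannot explain .28 in both places. It also departs from the two-sided level in B.1.

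**Step 4: what enrichment would have to deliver.** For r = .28 at 80% power, complicated delirium would need to be about 12.7% to 16.4% at N=400, or 9.9% to 12.2% at N=460. Dividing by 0.33 gives delirium rates of about 38% to 50% and 30% to 37%. The rate entered is 24%.

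**Step 5: the Aims 1b and 2a probability.** Two readings are possible.

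- Independent draws with true r = .54, by Fisher z with standard error 1/√(n - 3): atanh(.48) = 0.523, atanh(.54) = 0.604, atanh(.60) = 0.693. The standard errors are 0.0518 (n=375) and 0.0741 (n=185). The probabilities are 0.898 and 0.748, with product 0.67.
- Random splits of a fixed cohort of 560 whose own correlation is .54, by simulation: about 0.84 for both parts together.

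**The case against.** Three points can be made for the plan.

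First, power and predictor prevalence are unstated in Project 4, so the two-decimal values rest on supplied inputs. That is fair, and the exact replacement figure depends on them. The direction does not: any setting that gives .28 at N=560 gives more at N=400. Reporting .28 for both would need a different power or test for each aim, and the text mentions none.

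Second, the cohort has grown to 460. This shrinks the gap but does not close it. The minimum detectable value is still about 0.30 to 0.31, so for this figure the assurance in B.1.2 that stated power will be exceeded does not hold under these assumptions.

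Third, little hangs on the number. The sample sizes were set largely by feasibility. B.2.3 judges Aim 3a by sensitivity, specificity, predictive values and agreement. Aim 3a's own conclusion, that it can replicate medium to large effects, reads much the same at .30 as at .28. This stands and limits the weight of the point.

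A reader might also infer that Project 4's planning figures fail generally, and that the 80% claimed in Aims 1b and 2a should be 67% because the n=185 sample alone falls below 80%. The Protocol does not support that. Aim 2c reproduces. For Aims 1b and 2a, the Monte Carlo set-up is not described. The 67% assumes two independent draws from a wider population, whereas B.2.3 (Project 4, Aim 1b) describes a 67%/33% division of the existing 560 patients. Under that reading the joint probability is about 0.84, and 80% is slightly cautious.

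**Conclusion.** Aim 3a's .28 is wrong as written for N=400 at 7.9% complicated delirium, and it is not rescued by the enlarged cohort. Under two-sided 5%, an assumed 80% power and predictor prevalence of 20% to 50%, the figure should be about 0.32 to 0.33 at N=400 or 0.30 to 0.31 at N=460. At N=460 the chance of missing a true association of .28 is about 25% to 28% (1 - 0.75 to 1 - 0.72), rather than 20%.

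The error is confined to this one figure. The 80% probability in Aims 1b and 2a lies between the results of two plausible set-ups (0.67 and 0.84), so it is not shown to be wrong. The practical effect is minor: no test, recruitment target or success criterion rests on .28.

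**What to change.** In B.1.3, Project 4, Aim 3a, do one of two things:

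- Restate the minimum detectable tetrachoric correlation as about 0.30 to 0.31 for N=460 (0.32 to 0.33 if N=400 is kept), and state the power and predictor prevalence assumed.
- Enter the higher delirium prevalence that the enrichment argument relies on, justify it, and recompute.

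Leave Aim 2c's .28 as it is. Do not replace the 80% in Aims 1b and 2a with 67%.

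The cost is one corrected number and a sentence of assumptions. Nothing in the design, sample size or analysis changes.
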